## **10. Data Security**

Subject information will be stored electronically and controlled by the Principal Investigator. Identifiers will be separated from medical information and other data and will be replaced with a linkage code. Access to Protected Health Information (PHI) contained within the data base will be restricted to ZHH investigators.

Information linking the linkage codes to the subjects' PHI will be stored in a secure location in a locked file cabinet in the locked study coordinator's office separate from the medical information. Access to the information linking the linkage codes with each subject's respective PHI will be granted only to study personnel on a need to know basis as approved by the principal investigator of this study.

Data will be stored in the database for an indefinite period of time.

Data will be analyzed by the Zucker Hillside Hospital Department of Psychiatry Research Biostatistics Unit.

### **11. Benefits**

Subjects receiving ketamine anesthesia may require fewer ECT sessions to achieve remission and may have less cognitive side effects as compared to commonly used methohexitol anesthesia.

The results of this pilot study will guide us to design a larger and more definitive study and apply for NIMH funding.

### **12. Financial Disclosures**

The ECT procedures will be billed to the insurance carriers of the research subjects. There will be no reimbursement for participating in the study.

### **13. Data Analysis**

To test whether the time to remission is different between the ketamine and the methohexitol groups, a survival analysis will be performed. The outcome event will be remission, and Kaplan-Meier curves will show the percent of patients not in remission as a function of time on study. A log-rank test will be used to test for differences between the time to remission in the two groups. Patients who drop out of the study prior to achieving remission or who continue to the end of the study period without achieving remission will be analyzed as censored at the time of last observation.

For Aim 1, to test whether the rate of change in the HRSD score over time is different in the two treatment groups, a mixed model for longitudinal data will be used. The fixed effects are

treatment group and time on study, and the random effect is subject. The data will be examined to see whether a linear function of time is appropriate. If not, either the data will be transformed to achieve linearity, or another form (e.g., quadratic) of model will be considered. This model will yield estimates for slopes (rates of change in HRSD scores per visit) for each treatment group, and the groups will be compared by testing whether the slopes are significantly different from one another.

For Aim 2, to test whether the rate of change in the various measures of cognitive function over time is different in the two treatment groups, a mixed model for longitudinal data will be used for each of the measures. As above, the fixed effects are treatment group and time on study, and the random effect is subject. The data will be examined to see whether a linear function of time is appropriate. If not, either the data will be transformed to achieve linearity, or another form (e.g., quadratic) of model will be considered. As above, the model will provide estimates of the slopes measuring the rates of change in scores per visit for the two treatment groups; and the treatments will be compared by testing for a difference between the slopes corresponding to the two groups.

Since this is a pilot study, the goal is to estimate the magnitude of the effect sizes for use in designing a subsequent study. With 12 patients randomized to each of the two treatment groups, there is only 45% power with an alpha level of 5% to detect a difference of 50% remission rate in the methohexital group and an 80% remission rate in the ketamine group at visit 8. For the other aims, which look at the change in scores on various rating scales over time, there will be 80% power with an alpha level of 5% (2-sided) to detect a difference between the slopes (measuring rate of change in scores on tests per visit) for the two treatment groups of magnitude  $0.05\sigma$ , where  $\sigma$  is the standard deviation of scores in either treatment group at a single visit. If, for example, the standard deviation of the HRSD scores is 5.0, then there will be power to detect an increased rate of improvement in the ketamine group of 0.25 points per visit, corresponding to an average improvement of 2.0 more points per 8 visits in the ketamine group than whatever improvement is observed in the methohexital group (Diggle et al 1995).

Given the recognition that, with the small sample size, power will be low, the primary focus of analysis is to determine whether ECT with ketamine anesthesia compared to ECT with methohexital anesthesia produces a clinically significant effect, i.e., one that, even if it does not reach statistical significance, would justify a larger clinical trial to replicate effect size. We expect a mean number of 8 treatments to remission based on the results of a Consortium for Research in ECT paper.

Our specific hypothesis is that ECT will decrease functional connectivity in the Default Mode Network (time-wise hypothesis). We also think that the decrease in the expression of this network will correlate with the effectiveness of the ECT, or at least will show a difference

between responders and non-responders (group-wise hypothesis). In order to detect network changes, we will calculate seed based correlation, ICA network expressions and amplitude measures of the networks.

For Aim 2 B, Block and event related functional MRI designs will be analyzed with the standard General Linear Model implemented in both SPM (<http://www.fil.ion.ucl.ac.uk/spm/>) and FSL ([www.fmrib.ox.ac.uk](http://www.fmrib.ox.ac.uk)). For functional connectivity we will use seed-based correlation analysis, based on previously identified seed regions, and model-free ICA, using temporal concatenation to generate group-level components and dual regression to generate individual participant maps. For amplitude measures at each voxel we will use FFT-based ALFF and its normalized variant fALFF.

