### **Primary outcome**

The primary outcome will be the time to achieve remission. Remission is defined as two consecutive HRSD24 scores < 10, and HRSD24 total score does not increase > 3 points on the second consecutive HRSD24, or remains < 6 at the last two consecutive treatments. HRSD-24 scores are used to define remission.

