### 1. Study Overview

This is a prospective, random assignment, double blind, parallel group pilot study comparing the efficacy of bifrontal ECT performed with ketamine anesthesia to that performed with methohexitol anesthesia in patients with a major depressive episode. We intend over a 2 year period, to recruit 24 patients who are scheduled to receive an acute course of ECT. Patients who are able and willing to provide written informed consent will be randomly assigned on a 1:1 ratio to receive either a course of bifrontal ECT using ketamine or methohexitol anesthesia. Subjects will receive a standard acute course of ECT (3X/week) and depressive symptomatology will be monitored with the Hamilton Rating Scale for Depression (HRSD-24) before each treatment.

The primary outcome will be the number of treatments needed to achieve remission. Remission is defined as two consecutive HRSD scores  $\leq 10$ , and HRSD total score does not change  $> 3$

points or remains < 6 at the last two consecutive treatments. For the secondary aim of this pilot study we will monitor cognitive changes before and after each ECT treatment, and at the end of the treatment course. In addition, we will collect data on other treatment parameters such as seizure duration, electroencephalogram (EEG) morphology, hemodynamic changes, and emergence of any psychotic symptoms post treatment.

Parallel with these procedures we will also collect magnetic resonance imaging (MRI) data on these subjects. The timeline of neuroimaging and its relation to ECT is illustrated in Figure 1.

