## **3. Inclusion/ Exclusion Criteria**

Inclusion Criteria for patients:

1. Male or female subjects 18 to 70 years of age

2. DSM IV diagnosis of Major Depression (296.3), unipolar without psychotic features or Bipolar I or Bipolar II Depression without psychotic features confirmed by SCID-IV interview
3. Pretreatment 24-item Hamilton Rating Scale for Depression score  $\geq 21$
4. Subjects must have an initial score of at least 20 on the MADRS at screen
5. ECT is clinically indicated
6. Patient is competent to provide informed consent

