#### **4. Randomization**

**Method:** The permuted block method of randomization will be used to assign patients to one of the treatment conditions. Block size will be varied to minimize the likelihood that the blind will be broken by raters who are blind to assessment. For safety purposes the anesthesiologist and

the ECT psychiatrist will not be masked to the anesthetic agent used. Randomization will be performed by the research coordinator and will be communicated to the ECT psychiatrist and the anesthesiologist.

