### d. Outcome Criteria

## **1. Remitter criteria**

- (a)  $\geq 60\%$  decrease from baseline in HRSD total score, *and*
- (b) HRSD  $\leq 10$  on two consecutive ratings, *and*
- (c) HRSD does not change  $> 3$  points on last 2 consecutive treatments. We do not define a specific minimum or maximum number of ECT for a patient to be classified as a remitter.

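### The primary log-rank test takes no account of baseline HRSD-24, and no effect estimate is named for time to remission; a baseline-adjusted hazard ratio should be pre-specified

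*Combined protocol and SAP*

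**What the plan says.** The Primary outcome section states: "The primary outcome will be the time to achieve remission". Section 13 compares the arms with Kaplan-Meier curves and a test: "A log-rank test will be used to test for differences between the time to remission in the two groups". No covariate, stratification, hazard ratio or other effect estimate is given for this outcome. The same section says that the pilot is meant to supply effect sizes for designing the next study.

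On allocation, section 1 has patients "randomly assigned on a 1:1 ratio", and section 4 says: "The permuted block method of randomization will be used to assign patients to one of the treatment conditions". Block size varies, and no stratification factor is named.

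On severity, section 3 admits patients with a "Pretreatment 24-item Hamilton Rating Scale for Depression score" of at least 21 and sets no upper limit. Remission is an HRSD of 10 or less in the Study Overview, in ECT Procedures and in the Remitter criteria, and below 10 in the Primary outcome section. The Remitter criteria require it "on two consecutive ratings" and, alone among these places, add a fall of at least 60% from baseline. These definitions must be reconciled, but the present point holds under each of them.

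Table 2 schedules the HRSD-24 at baseline for every patient.

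**The concern.** The distance a patient must travel to count as remitted depends on where that patient starts. Baseline score is therefore likely to predict time to remission. It is recorded in everyone, yet it is used neither in the allocation nor in the primary comparison.

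With 12 patients per arm, an appreciable chance difference in starting severity is an ordinary event. The trial will be read mainly for the size of its observed effect, because section 13 concedes low power and looks for an effect that could justify a larger trial even without significance. An effect estimate that moves with a chance imbalance is a poor input to that decision. The plan also leaves open which estimate will be used, so the choice to adjust could be made after the imbalance is seen.

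**Working it through.** **1. The plan's own power figure.** Section 13 says: "With 12 patients randomized to each of the two treatment groups", "there is only 45% power with an alpha level of 5" per cent, for remission of 50% against 80% at visit 8.

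- Two proportions, one-sided: Φ[(0.30 − 1.645·√(2·0.65·0.35/12)) / √((0.25 + 0.16)/12)] = 45.6%. This reproduces the stated 45%.
- The same formula, two-sided: 32.9%.
- Log-rank (Schoenfeld), two-sided: hazard ratio ln 0.2 / ln 0.5 = 2.32; events 12·0.5 + 12·0.8 = 15.6; Φ(√15.6/2 · ln 2.32 − 1.96) = 38%.

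So 45% is a one-sided figure for proportions at visit 8. The plan does not state its sidedness, which is a separate matter to clarify.

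**2. Fall needed for remission.** Under the Remitter criteria the fall from baseline B is max(0.6B, B − 10):

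- B = 21: 12.6 points
- B = 25: 15 points
- B = 40: 30 points

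The 60% rule binds only for baselines from 21 to 25; above that the absolute cut-off does. With the 10-or-less cut-off alone, the falls at 21 and 40 are 11 and 30 points.

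**3. Chance imbalance.** The standard error of the difference in baseline means is √(2/12) = 0.41 SD, so P(|difference| ≥ 0.5 SD) = 2[1 − Φ(0.5/0.408)] = 22%. The plan gives no baseline SD. With its illustrative HRSD SD of 5.0, one standard error is 2.04 points and P(|difference| > 2 points) = 33%. With an SD of 4 or 7 (assumed) that probability is 22% or 48%.

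**4. Effect on the estimate and the test.** The documents give no association between baseline and remission, so it is assumed as a log hazard ratio per baseline SD. About 3,000 trials per row were simulated: 12 per arm, exponential times, 50% control remission by visit 8 at mean baseline, conditional hazard ratio 2.32. The factor is what a one-standard-error imbalance (0.41 SD, about 2 points), with ketamine patients the more severe, does to the hazard ratio. Hazard ratios and factors are for visit 8. Power is two-sided, log-rank v adjusted Cox.

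| Log HR per SD | HR, unadjusted / adjusted | Factor, unadjusted / adjusted | Power, visit 8 | Power, visit 15 |
|---|---|---|---|---|
| 0 | 2.32 / 2.40 | 0.99 / 0.99 | 37 v 35% | 45 v 43% |
| −0.25 | 2.30 / 2.43 | 0.90 / 1.00 | 36 v 35% | 43 v 44% |
| −0.5 | 2.15 / 2.39 | 0.83 / 1.02 | 32 v 34% | 36 v 41% |
| −0.75 | 2.01 / 2.45 | 0.77 / 1.02 | 27 v 34% | 31 v 40% |

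A hand check, exp(−0.5·0.408) = 0.82, agrees with the simulated 0.83. An imbalance the other way gives the reciprocal. In the −0.5 row the unadjusted hazard ratio would read 2.15·0.83 = 1.78 or 2.15/0.83 = 2.59, depending only on which arm drew the more severe patients.

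- Standard error of the log hazard ratio: it rises with adjustment, from 0.53 to 0.55–0.57 at visit 8 and from 0.47–0.48 to 0.49–0.51 at visit 15.
- Type I error: about 5–6% for the log-rank test at every prognostic strength, and about 4–6% for the adjusted Cox model.

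**5. A different model.** HRSD trajectories were simulated and scored with the Remitter criteria (400 trials per scenario; trajectory parameters assumed).

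- In one set, the rule itself produced a log hazard ratio of −0.23 to −0.33 per SD when scores fall in proportion to baseline, and −0.49 to −0.72 when they fall by a fixed amount per session.
- In that set a 2-point imbalance multiplied the unadjusted hazard ratio by 0.91–0.95 (proportional) or 0.83–0.88 (fixed), against 0.99–1.09 adjusted. Power was 36 v 38% and 32 v 34% (proportional), and 20 v 29% and 22 v 33% (fixed).
- A second set gave 0.84–0.95 unadjusted and 0.96–1.06 adjusted, with power of 40–43% v 44–47%.
- Adjusted type I error was 3–7% over both sets.

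**The case against.** **The test is valid.** A reader might infer that chance imbalance biases the primary test. It does not: under randomization it is sampling variation, and the log-rank test holds its type I error. The largest shift above, ln 0.77 = −0.26, is about half of one standard error (0.53). This objection stands in full. What remains is accuracy given the imbalance that actually occurs.

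**Precision.** A reader might infer that ignoring baseline widens the interval. For a hazard ratio the reverse holds: the standard error rises slightly with adjustment. Any power gain comes from an adjusted hazard ratio that lies further from 1.

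**Large power gains.** A scenario can be built in which adjustment lifts power from 55% to 83%. It needs an assumed baseline mean of 32, an SD of 7 and a fixed fall per session, none of which the documents support. With proportional decline the gain is 1–2 points. In a wider set of scenarios gains ran from 1 to 24 points, and those above 14 needed a fixed fall with little variation between patients (log hazard ratio −0.8 to −1.1 per SD).

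**No hazard ratio is planned, and the planning effect is a pair of proportions.** Both are true, and a hazard ratio conditional on baseline does not convert directly to 50% against 80%. But with no estimate named at all, the plan does not deliver the effect size it promises. The Kaplan-Meier curves can still supply the proportions.

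**The HRSD mixed model.** Its subject effect absorbs starting severity, but it compares slopes and does not touch time to remission.

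**Few events and many ties.** About 16 events by visit 8 is thin for two parameters, and remission can be recorded only at visits. Both limit the fix to one covariate and a stated tie method.

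**Conclusion.** The point holds as a recommended improvement, not as a fault that invalidates the analysis. The log-rank test is sound. The gap is that a trial run to estimate an effect names no estimate for its primary outcome and leaves out the one baseline measure on which remission directly depends.

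If baseline HRSD-24 is prognostic at a log hazard ratio of −0.25 to −0.75 per SD, a 2-point imbalance multiplies an unadjusted hazard ratio by about 0.77–0.95, and an adjusted one by about 0.96–1.09. The change in power runs from about −2 points to roughly +10 under most assumptions, and is larger only if baseline is very strongly prognostic. If baseline is not prognostic, adjustment costs about 2 points and gains nothing.

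All of these sizes rest on assumed prognostic strength and trajectories. The 22% chance of a 0.5 SD imbalance does not; it follows from 12 patients per arm. The documents do not support a claim of bias, of lost precision or of a large power loss.

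**What to change.** In Data Analysis (section 13), pre-specify a Cox model for time to remission with treatment arm and continuous baseline HRSD-24, using Efron or exact handling of ties. Report its hazard ratio and 95% CI as the treatment-effect estimate. Keep the Kaplan-Meier curves and the unadjusted log-rank test beside it.

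The cost is a few sentences in the plan; no new data, patients or procedures are needed. There are four downsides:

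- The hazard ratio is conditional on baseline, so it must be described as such when used for planning.
- Its standard error is slightly larger.
- In the exponential simulations the adjusted hazard ratio averaged about 2.4 against a true 2.32, a small upward drift to keep in mind.
- About 16 events by visit 8 support this one covariate and no more.

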### **6. ECT Procedures**

ECT will be administered following the standard 3 times per week schedule (Monday, Wednesday, Friday) until remission is achieved (defined by an HRSD-24 score of 10 or less) or until a patient is declared a non remitter (see criteria, page 15). Subjects will be withdrawn from the study if side effects become limiting, or if either the patient or principal investigator determine that ECT should be discontinued. All patients will be treated with moderately suprathreshold stimulus doses. Threshold will be determined at the first treatment and doses will be increased at subsequent treatments as needed to insure adequacy of seizures. (see section d) The average total number of ECT per patient is expected to be approximately 8 and will not exceed 15 in any case.

Both inpatients and outpatients will be brought to the ECT treatment area in the morning on the day of treatment and an intravenous catheter will be introduced and remain in place until the treatment has been completed. Blood pressure, pulse rate, ECG, and pulse oximetry will be monitored prior to anesthetic induction and continuously during the procedure.

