## **2. Non-remitter criteria**

- (a) patient does not reach above remission criteria, *and*
- (b) has at least 10 treatments, *and*
- (c) reaches a plateau defined as no clinical improvement ( $< 3$  point decrease in HRSD after last 2 consecutive treatments).

*Drop-outs* are patients who discontinue treatment before they can be declared remitters or *non-remitters*. Premature exits in this study will be analyzed as non remitters. Criteria for *premature exits* are as follows:

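### Censoring declared non-remitters at their last rating makes the Kaplan-Meier curve overstate remission after treatment 10; the visit-8 contrast is untouched and the log-rank test barely moves

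*Combined protocol and SAP*

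**What the plan says.** Section 6, ECT Procedures, continues ECT until remission "or until a patient is declared a non remitter", and the number of treatments "will not exceed 15 in any case". Under the non-remitter criteria in section 7d, such a patient has not met the remission criteria, "has at least 10 treatments", and "reaches a plateau defined as no clinical improvement", meaning an HRSD fall of less than 3 points after the last two treatments. A plateau stop can therefore come at any treatment from 10 onward. Drop-outs are a different group: they "are patients who discontinue treatment before they can be declared remitters or" non-remitters.

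Section 13, Data Analysis, takes remission as the event and says "Kaplan-Meier curves will show the percent of patients not in remission as a function of time on study". The primary test follows: "A log-rank test will be used to test for differences between the time to remission in the two groups". One rule covers everyone without remission. Those who drop out, and those who "continue to the end of the study period without achieving remission will be analyzed as censored at the time of last observation", are handled alike. A declared non-remitter is not a drop-out, so falls in the second group. The end of the study period is not defined, but on any reading these patients are censored at their last rating. There is no competing-event rule, and nothing carries declared non-remitters forward to the cap.

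The same section gives the pilot's goal as estimating effect sizes for the design of a later study.

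**The concern.** Kaplan-Meier treats a censored patient as having the same later chance of the event as those still at risk. Here the patient is censored because of the outcome: the score has stopped falling, ECT ends, and remission within the course is no longer possible. Those who stay at risk after treatment 10 are, by rule, those who did not meet the plateau test. When one of them remits, the product-limit estimate credits a share of that remission to patients already declared failures. Past treatment 10 the curve is then no longer the percentage of patients not in remission, which is what section 13 says it will show.

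At stake is the late part of the curve and any end-of-course remission rate read from it to plan the next trial. The error grows with the share of patients stopped at a plateau, so at the plan's rates it is larger in the methohexital arm and narrows the apparent late difference.

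**Working it through.** Visit n is read as treatment n throughout.

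**1. The plan's own figure.** Section 13 gives 45% power for 50% versus 80% remission at visit 8, with 12 per arm and alpha 5%. The pooled two-proportion formula, one-sided, gives z = [0.30 - 1.645 x sqrt(2 x 0.65 x 0.35/12)] / sqrt[(0.25 + 0.16)/12] = (0.300 - 0.320)/0.185 = -0.11, so power is 45.6%. The two-sided version gives 32.9%; the plan does not state sidedness for this figure. No plateau stop can occur before treatment 10, so a visit-8 contrast does not depend on the censoring rule.

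**2. One arm of 12 (assumed pattern).** Six remit by treatment 8, k are stopped at a plateau at 10, and one remits at each of 11 and 12. Observed remission is 8/12 = 66.7%. With n = 6 - k at risk after 10, S = 0.5 x (n - 1)/n x (n - 2)/(n - 1) = 0.5 x (n - 2)/n.

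| k | S | 1 - KM |
|---|---|---|
| 1 | 0.5 x 3/5 = 0.300 | 70.0% |
| 2 | 0.5 x 2/4 = 0.250 | 75.0% |
| 3 | 0.5 x 1/3 = 0.167 | 83.3% |
| 4 | 0.5 x 0/2 = 0 | 100% |

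If the k patients stay at risk, n = 6 and S = 0.5 x 4/6 = 0.333, so the curve reads 66.7%, as observed.

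**3. Expected size at the plan's rates, simple model.** Assume a constant remission hazard per treatment, h = 1 - (1 - p8)^(1/8): 0.083 for methohexital (p8 = 0.5) and 0.182 for ketamine (p8 = 0.8). Assume also a plateau-stop probability q after each of treatments 10 to 14. The documents give no value for q, so it is varied from 0.1 to 0.5.

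- 1 - KM at 15 = 1 - (1 - h)^15.
- Actual cumulative remission = 1 - (1 - h)^10 + h x sum over t = 11 to 15 of (1 - h)^(t - 1) x (1 - q)^(t - 10).

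| q | Methohexital: KM / actual | Excess | Ketamine: KM / actual | Excess |
|---|---|---|---|---|
| 0.1 | 72.7 / 69.0 | 3.7 | 95.1 / 93.1 | 2.0 |
| 0.2 | 72.7 / 66.2 | 6.5 | 95.1 / 91.6 | 3.5 |
| 0.3 | 72.7 / 64.0 | 8.7 | 95.1 / 90.4 | 4.7 |
| 0.5 | 72.7 / 61.1 | 11.6 | 95.1 / 88.7 | 6.4 |

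At treatments 8 and 10 the two estimates are identical. If the hazard halves after treatment 10, the excess is 2-6 points (methohexital) and 1-4 (ketamine). At q = 0.3 in both arms, the late difference reads 95.1 - 72.7 = 22.4 points against an actual 90.4 - 64.0 = 26.4. This model leaves out selection: patients are stopped regardless of how they were improving.

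**4. Simulating the remitter and non-remitter rules, cap 15, arms of 12 (10,000 arms per scenario).** Assumed: baseline HRSD mean 32, SD 5; exponential decline; rating noise SD 2-3; decline rates and floors also assumed. Scenarios are grouped by the visit-8 remission they produce.

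- Visit-8 remission about 45-55%: mean excess 5-8 points, exactly zero in 51-72% of arms.
- Visit-8 remission about 74-82%: mean excess 1-2 points, exactly zero in 84-92% of arms.
- If a patient with a score of 10 or less may await the confirming rating before being called plateaued: 8-10 and 1-2 points.
- Large-sample bias near the methohexital rate, literal rule: 12-21 points.

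A repeat gave about 5 points near 50% and 1 point near 76%. Small arms average less than the large-sample figure because often nobody remits after a plateau stop, and then the curve does not move.

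**5. Log-rank test.** Simulated two-sided power under the step 3 model, censoring at the plateau versus carrying to 15: 44.1% versus 44.0% (q = 0.2) and 42.9% versus 42.7% (q = 0.4).

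**The case against.** The strongest reply is that little the plan commits to is affected. Its only stated remission contrast is at visit 8. The primary test is the log-rank, whose power hardly changes. Section 13 plans neither a median nor an end-of-course Kaplan-Meier estimate. Completers are also classified as remitters or non-remitters, so the raw proportion is available beside the curve. In arms of 12 the error is often exactly zero. All of this stands, and it limits the point to the curve after treatment 10. It does not make that part of the curve right, and the curve is the plan's stated display of remission over time in a pilot meant to yield effect sizes.

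A reader might infer more than the documents support:

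- That the curve will be wrong by 16-34 points. Such figures come from single simulated cohorts of 20,000 with 31-58% remission by treatment 15, mostly below what the plan's visit-8 rates imply. In arms of 12, even low remission (36-56% by treatment 15) gives a mean of 8-12 points.
- That a reading of 100% against 67% is typical. It needs everyone left at risk after the plateau stops to remit; with one or two stops the arm in step 2 reads 70% or 75%.
- That the median time to remission is distorted. It moves only if fewer than half of an arm remit by treatment 10, which is not what the plan assumes.

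**Conclusion.** The point holds for the Kaplan-Meier curve after treatment 10. The direction follows from the rules: whenever another patient in the arm remits after a plateau stop, the curve overstates remission during the course. The size rests on assumptions, because the documents give no plateau rate. At the plan's rates and 12 per arm, a mean of about 5-10 points (methohexital) and 1-2 points (ketamine) is reasonable, with no error in many arms and a large one in a few.

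It would be tempting to conclude that the primary test is invalid or the power figure wrong. The documents do not support that. The visit-8 contrast, the 45% figure and any median reached by treatment 10 are unaffected, and the log-rank result is essentially unchanged in the scenarios tried, although those did not link plateau to later prognosis. The amendment is worth making because it is cheap and protects a figure likely to be carried into the next trial.

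**What to change.** Add one sentence to section 13: a patient declared a non-remitter under section 7d stays in the risk set as not remitted to the 15-treatment cap, or the equivalent study day, and is censored there. Alternatively, report cumulative incidence with the declaration as a competing event; the two curves coincide if nobody else is censored before the cap. State that the rule applies to both the curve and the log-rank test, and keep the present rule as a sensitivity analysis.

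This needs no new data and no change to treatment. It assumes that declared non-remitters would not have remitted by treatment 15, which the plan's own label already implies, and it makes the reported remission figures less favourable.

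Drop-outs and premature exits are a separate matter that this sentence does not settle. The non-remitter criteria analyse premature exits as non-remitters, while section 13 censors drop-outs; those two passages must be reconciled. Until they are, the corrected curve equals the observed proportion remitted only where there is no other censoring.

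### The slope comparisons for HRSD and the repeated cognitive measures name subject as the only random effect; if patients' true rates of change differ, the standard error is too small and the test exceeds 5%

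*Combined protocol and SAP*

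**What the plan says.** Section 13 uses a longitudinal mixed model for HRSD (Aim 1) and repeats it for each cognitive measure (Aim 2). The effects listed are "treatment group and time on study, and the random effect is subject". The model is to yield one slope per arm, and "the groups will be compared by testing whether the slopes are significantly different from one another". If a straight line does not fit, the data may be transformed or another form of time, such as a quadratic, considered. No random slope, serial or unstructured covariance, robust standard error or small-sample degrees of freedom is mentioned. The repeated-measures ANOVA described later is for imaging only.

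The power paragraph states that "there will be 80% power with an alpha level of 5% (2-sided) to detect a difference between the slopes" of 0.05 sigma per visit, where sigma is the SD of scores at a single visit. With an SD of 5.0 this is 0.25 HRSD points per visit. The same paragraph says that for this pilot "the goal is to estimate the magnitude of the effect sizes for use in designing a subsequent study".

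Section 7b has HRSD rated at baseline and before each treatment, MMSE before each session, and reorientation after each session. The rest of the neuropsychological battery has three time points, except WRAT-3, which is given only at baseline and has no slope. The number of treatments is "expected to be approximately 8 and will not exceed 15 in any case" (Section 6).

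**The concern.** A model with only a random intercept lets patients start at different levels but gives all patients in an arm the same true rate of change. Any real spread in slopes is then treated mostly as independent residual noise. It is averaged over all ratings, when it should be averaged over only 12 patients per arm. The reported standard error is then too small, the interval too narrow, and the test rejects too often.

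This analysis serves the temporal-pattern part of the primary aim and the repeated cognitive measures of Secondary Aim A. What is at stake is mainly the stated precision of the slope results, in a pilot whose purpose is to inform the design of a later study.

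**Working it through.** **1. The plan's slope power.** With a random intercept only, equal visit spacing and n = 12 per arm, the detectable difference d satisfies d² = 2(1.96 + 0.84)² σ²(1 − ρ)/(n·Sxx), where Sxx = m(m² − 1)/12 for m ratings. Section 13 gives d = 0.05σ but neither ρ nor m, so the formula is solved for ρ: 1 − ρ = 12·Sxx·0.0025 / [2(1.96 + 0.84)²].

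| Ratings m | Sxx | ρ needed for 80% power |
|---|---|---|
| 8 | 42 | 0.92 |
| 9 | 60 | 0.885 |
| 10 | 82.5 | 0.84 |
| 12 | 143 | 0.73 |
| 15 | 280 | 0.46 |
| 16 | 340 | 0.35 |

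The stated 80% is attainable under some of these pairs, so it can be neither confirmed nor refuted.

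**2. Standard error when slopes differ.** Let s be the between-patient SD of true slopes and r the residual SD. With equal courses:

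- True variance of the slope difference: (2/12)(s² + r²/Sxx).
- Variance reported by the random-intercept model, approximately: (2/12)(s²/(m − 1) + r²/Sxx).

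The second is smaller than the first whenever s > 0. The documents give neither s nor r, so every value below is an assumption. As a rough anchor, a 60% fall from the entry floor of 21 over 8 treatments is 12.6/8, about 1.6 points per visit. If non-remitters improve by 0.3 to 1.2 per visit (assumed) and 50-80% remit, a two-group mixture gives s from √(0.8 × 0.2) × (1.575 − 1.2) = 0.15 to √(0.5 × 0.5) × (1.575 − 0.3) = 0.64.

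For m = 9 (visits 0-8, Sxx = 60) and r = 4, with the common factor 2/12 left out:

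| s | True: s² + 16/60 | Reported: s²/8 + 16/60 | Ratio | Type I error, 2[1 − Φ(1.96/√ratio)] | Simulated |
|---|---|---|---|---|---|
| 0 | 0.267 | 0.267 | 1.00 | 5.0% | 5% |
| 0.15 | 0.289 | 0.269 | 1.07 | 5.9% | 5.9% |
| 0.25 | 0.329 | 0.274 | 1.20 | 7.4% | 7% |
| 0.5 | 0.517 | 0.298 | 1.73 | 13.7% | 14% |
| 0.65 | 0.689 | 0.319 | 2.16 | 18.2% | 18-19% |

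The simulations used 40,000 trials per setting. A t-test on per-patient slopes (22 df) stayed at about 5% throughout.

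**3. Sensitivity.** With r = 1.69, the value that makes the plan's 80% hold at 9 ratings with σ = 5 (√[25 × 0.115]), type I error is about 10%, 16% and 32% at s = 0.16, 0.25 and 0.5. For the three-point battery at visits 0, 4, 8 or 0, 4, 11, with r from 0.339σ to 0.632σ and s from 0.025σ to 0.2σ, it is about 5-17%.

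**4. Unequal courses.** Courses were ended by the plan's remitter and non-remitter rules with a maximum of 15 ECT, assuming a mean baseline of 27, a mean fall of 2.6 per visit and r = 4 (1,500 trials per setting):

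| s | Planned test | Random slope, Kenward-Roger | Patient-slope t-test |
|---|---|---|---|
| 0 | 4% | 2% | 5% |
| 0.25 | 10% | 4% | 5% |
| 0.5 | 20% | 5% | 5% |
| 0.65 | 30% | 6% | 6% |

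**5. Power.** At the 9-rating calibration (σ = 5, r = 1.69) and a difference of 0.25 per visit, the planned test has 80% power and the patient-slope test 76% when s = 0. If s is 0.25 or 0.5, the patient-slope test has 42% or 19%.

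**The case against.** The strongest reply is that the model sentence is shorthand. It lists no group-by-time term either, yet a comparison of slopes needs one, so it may name factors and not every term. On that view, subject as a random effect could include a patient-level slope. This leaves the intent uncertain. Even so, nothing in the documents supplies a random slope, and an analyst following the text would ordinarily fit a random intercept.

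A reader might infer that the plan's own rules show that slopes differ: treatment continues "until remission is achieved (defined by an HRSD-24 score of 10 or less) or until a patient is declared a non remitter", the remitter criteria say "We do not define a specific minimum or maximum number of ECT for a patient to be classified as a remitter", and a non-remitter is one who "reaches a plateau defined as no clinical improvement" after at least 10 treatments. They do not show it. Under the assumptions of step 4, these rules give almost the same spread of course lengths when every patient has the same true slope (mean 10.1 ratings, SD 1.8) as when the slope SD is 0.5 (mean about 10.1, SD 1.9). Differing response is plausible on clinical grounds, not established by these rules.

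It also stands that the size depends wholly on assumed SDs and is slight at the low end. The upper end sits less easily with the plan's single sigma. With r = 4, holding the SD at 5 at visits 0 and 8 when s = 0.65 needs an intercept-slope correlation of −4 × 0.65/√(25 − 16) = −0.87; with zero correlation the visit-8 SD is √(25 + 64 × 0.4225) = 7.2.

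Finally, this is a 24-patient pilot that puts effect size ahead of significance, and its log-rank analysis does not use this model.

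**Conclusion.** The point holds conditionally. As ordinarily read, the model understates the uncertainty of the slope difference if true slopes vary. The direction follows from algebra; the size does not follow from the documents. With 9 ratings, 12 per arm and residual SD 4, the illustrative type I error runs from about 6% to 18-19% over slope SDs of 0.15 to 0.65. It is higher with a smaller residual SD and lower for the three-point battery.

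The log-rank analysis is unaffected, and so are the slope point estimates when courses are equal. The main consequence is overstated precision in slope results meant to inform a later study.

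Two stronger readings are not supported. The slope power is not shown to be wrong, only unverifiable without ρ, the number of ratings and the slope SD. Nor can it be said that a later trial would be undersized by the variance ratios in step 2: that would require it to be powered on a slope using this model's variance, and the documents do not say so.

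**What to change.** - Write the model with group, time and group-by-time as fixed effects.
- For measures rated at each ECT (HRSD, MMSE, reorientation time), add a correlated random intercept and time slope per patient, with Kenward-Roger or equivalent degrees of freedom. If it does not converge, use a t-test on per-patient slopes; do not fall back to a random intercept alone.
- For the three-point battery, use the per-patient-slope test, which keeps the slope-per-visit quantity the plan asks for.
- Report the estimated slope SD as a pilot result.
- Restate the slope power with its assumed ρ (or residual SD), number of ratings and slope SD, preferably as a range.

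This costs analysis-plan wording and one recalculated power sentence; no new data are needed. The downsides are wider intervals, a possibly less favourable stated power and some convergence risk with 24 patients. If slopes do not in fact differ, the patient-slope test loses a little power (about 76% against 80% in step 5), and the Kenward-Roger test is conservative with unequal courses (about 2% in step 4).
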